#### 6.4.4 HAE Attack Requiring Therapy

The number of HAE attacks and the proportion of participants requiring on-demand therapy at baseline and during the treatment period will be summarized. The type of on-demand therapies used to treat HAE attacks will also be summarized.

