4.5. Duration of Treatment and Duration of Study

Individual participants will receive 1 dose of STAR-0215 (Cohort 1; Day 1) or 2 doses (Cohort 2; Days 1 and 84, and Cohort 3; Days 1 and 28). The duration of study participation for each participant, including the Screening and Run-In period, is up to [REDACTED], or [REDACTED] days in Cohorts 1, 2, and 3, respectively. The study is composed of 3 periods, as follows:

- Screening/Run-In: at least 56 days
- Treatment Period: Individual participants will receive STAR-0215 on Day 1 (Cohort 1), Day 1 and 84 (Cohort 2), or Day 1 and 28 (Cohort 3).
- Follow-up Period: approximately 6 months after the last dose of STAR-0215 (Day 168 for Cohort 1, Day 251 for Cohort 2, and Day 195 for Cohort 3). At this time, participants who are willing and eligible to consent can begin participation in the long-term open label extension study (STAR-0215-202).
- Follow-up Period: For participants who do not participate in the long-term open label extension study, monitoring will be performed through [REDACTED] months after the last dose of STAR-0215 in all cohorts (Day [REDACTED] in Cohort 1, Day [REDACTED] in Cohort 2, and Day [REDACTED] in Cohort 3) through regular contacts and scheduled study visit.

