#### 3.2 Secondary Endpoints - Efficacy

- Change from baseline in monthly HAE attack rate, overall and per month.
  - 50%, 70%, and 90% overall reduction of HAE attacks
  - Investigator assessed HAE Attack definition is given in Protocol section 7.12.1:

To be considered an HAE attack, the Investigator must confirm that the event has signs or symptoms consistent with an HAE attack that meet at least 1 of the following criteria: Peripheral angioedema, Abdominal angioedema, or Laryngeal angioedema.

Prodromal symptoms or participant-reported use of on-demand HAE attack treatment alone are not sufficient to define an event as an HAE attack.

Each HAE attack must be unique. To be distinct from the previous attack, the new symptoms must occur at least 24 hours after resolution of the prior attack's symptoms.

The HAE attack resolution is defined as the participant no longer having symptoms of the HAE attack. The HAE attack severity will be graded by the Investigator.
- Proportion of participants who are HAE attack free
- Incidence of at least one HAE attack by maximum severity (mild, moderate, and severe), including participants without any attacks.
- Duration of HAE attack (shorter than 12 hours, 12 to 24 hours, 24 to 48 hours, and longer than 48 hours).
- The number of HAE attacks requiring on-demand therapy.
- Time to first HAE attack after first and last dosing, censored to End of Study visit.
- HAE attack free days, from treatment start until End of Study.

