### 5.2 Data Conventions

- **Period definition:**
  - **Screening/Run-In Period:** Starts at the Screening visit until the day before first treatment, approximately Study Day -56 to -1. If a participant has an HAE attack during the Run-In period before Day 1, all signs and symptoms of the HAE attack must be resolved before dosing.
  - **Treatment & Follow-up Period:** The period from date of first dose to End of Study Date.
  - **End of Study Date:** The latest of date of Early Termination visit or as designated by “End of Study” CRF page.
  - **Treatment Period (for HAE assessments)** is defined in [Section 9.1](#); for this period the last scheduled visit for each cohort is Day 168 visit for cohort 1, Day 251 visit for cohort 2, and Day 195 visit for cohort 3. The last assessment date or last dose date can be used for participants that have not reached the end of their cohort’s treatment period.
  - **First Dose Period (for HAE assessments)** is defined as the first dose until participant’s second dose (cohorts 2 & 3) or end of treatment period.
  - **Study day:** Relative to the date of first treatment of STAR-0215: assessment date – first treatment date (+1 if assessment is after first treatment).
- **Conversion factors:**
  - 1 month = 30.4375 days
  - 1 year = 365.25 days
  - 1 week = 7 days
- **Additional rules**
  - (Absolute) Change from baseline = Value at the time point – Baseline value.
  - Relative change from baseline = [(Value at the time point – Baseline value) / Baseline value] x 100.

- % inhibition (of pharmacodynamic assessments) =  $1 - [\text{postdose rate} / \text{predose rate}] \times 100$ .
- Duration on Study = (End of Study Date – Date of First STAR-0215 treatment) +1.
- Duration of Treatment Period = (Last Treatment period assessment date – Date of First STAR-0215 treatment) +1.

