## 6.4 Efficacy Evaluation

All analyses of HAE attack data will be presented using the Efficacy Analysis Set. Both Run-In and Post-Treatment period will be displayed where applicable.

All HAE attacks that occurred on study will be listed for both Run-In and Treatment periods.

A summary of Run-In period HAE attack assessments will include Location of HAE attacks (Abdominal, Laryngeal, Peripheral); the baseline (Run-In period) values of: HAE attack rate, HAE attacks by worst severity (none/attack-free, mild, moderate, and severe), duration of each participants longest HAE attack, number and proportion of HAE attacks requiring on-demand therapy, and HAE Attack Free Days. This summary will be repeated for the first dose period.

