### 6.4.1 Change from Baseline in Monthly HAE attack rate

HAE attack rate will be expressed as the number of unique investigator-confirmed HAE attacks per month. Only unique (non-overlapping) HAE attacks will be counted; attacks are considered overlapping when a start date falls within 24 hours of an earlier attack's end date. The HAE attack rate will be calculated as:

$(\text{number of HAE attacks} / \text{duration of evaluation period in days}) * 30.4375$ ; where the duration of participants' run-in period and post-treatment follow-up periods is defined in [Section 9.1](#) and [section 5.2 \(Treatment period\)](#).

Change from baseline (Run-In period) to on treatment HAE attack rate, will be summarized by the absolute and percentage change from Baseline. Descriptive statistics (mean, median, standard deviation, Q1, Q3, minimum and maximum values) and 95% CI will be presented. The proportion of participants with a clinical response to treatment will be presented in increments as greater than or equal to 50%, 70%, and 90% reduction of HAE attacks.

A plot of individual participant's HAE attacks over time will display duration and severity by cohort. The plot will begin in the run-in phase through the last HAE assessment. The scheduled dose(s) of each cohort will be represented with dotted-lines. This plot will also be created by HAE attack location or overall cohort plot (combining participants).

HAE attacks per month (attack rate) will be presented at 4-week intervals (28 Days) from treatment start; first dose period, and 3 and 6 month intervals following last dose; and the first 3 and 6 months from Baseline (from initial dose) will also be provided. The mean monthly rate, change from baseline, and 95% CI will be presented; percent change will also be presented for monthly rates. Additional analysis of participants who have completed each interval may be performed.

Analysis of overall HAE attack rate or certain intervals, will be performed on sub-categories of HAEs: by HAE severities Mild, Moderate, Severe, and Moderate or Severe; and those that required therapy (“rescue medication”).

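### SAP 6.4.4 summarises on-demand therapy over run-in and treatment windows of unequal length: the count is not tied to the monthly rate planned in 6.4.1, and the participant proportion has no time-adjusted version

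*SAP*

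**What the plan says.** The secondary endpoint is a count, listed in SAP 3.2 as "The number of HAE attacks requiring on-demand therapy" and likewise in Protocol 3. SAP 6.4.4, the section headed for it, says: "The number of HAE attacks and the proportion of participants requiring on-demand therapy at baseline and during the treatment period will be summarized". It names no divisor.

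The two windows differ in length. SAP 6.2.2 makes the run-in the baseline for attack data. Protocol 4.5 gives its length as "Screening/Run-In: at least 56 days", and Protocol 4.1 lets it be extended after consultation, with no upper limit. SAP 5.2 sets the end of the treatment period: "the last scheduled visit for each cohort is Day 168 visit for cohort 1, Day 251 visit for cohort 2", and the Day 195 visit for Cohort 3. Participants who have not reached that visit contribute a shorter period.

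Two other parts of the SAP bear on the same endpoint:

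- SAP 6.4.1 defines a rate: "HAE attack rate will be expressed as the number of unique investigator-confirmed HAE attacks per month". Attacks are divided by days in the evaluation period and scaled with the SAP 5.2 conversion, "1 month = 30.4375 days". The same section says that analysis of the overall rate, or of certain intervals, "will be performed on sub-categories of HAEs: by HAE severities Mild, Moderate, Severe, and Moderate or Severe; and those that required therapy".
- SAP 6.4 plans a run-in summary that includes the attack rate and both how many attacks, and what share of them, needed on-demand treatment. It adds: "This summary will be repeated for the first dose period".

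**The concern.** There is no control group. SAP 6.1 makes each participant their own control, and Protocol 9.6 presents attack data in the same way for the run-in and treatment periods. Nothing is formally tested (SAP 6.2.1), so the side-by-side display is the evidence of effect for this endpoint.

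A count grows in proportion to the time observed, and the chance of needing therapy at least once also rises with time. Beside a window of about 56 days, a window three to four and a half times as long can make an effective drug look ineffective. The factor differs by cohort, so the by-cohort columns carry different distortions. The neighbouring endpoints are protected: the attack rate and the proportion of attack-free days are divided by evaluation time, and attack-free participants are also shown over fixed 3- and 6-month intervals. Section 6.4.4 has no such version and no cross-reference to one.

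**Working it through.** The plan states no expected number of treated attacks, sample size calculation or power, so there is no planned figure to reproduce.

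**Inputs.** Run-in R = 56 days (Protocol 4.5, a minimum). Treatment period T = 168, 251 and 195 days for Cohorts 1, 2 and 3 (SAP 5.2). First dose period in Cohorts 2 and 3: Day 1 to Day 84 = 83 days, Day 1 to Day 28 = 27 days. Month = 30.4375 days. Entry requires at least two run-in attacks (Protocol 5.1, criterion 9).

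**1. Raw count.** For a reduction r from the run-in rate, the ratio of expected counts is (T/R)(1 − r). The count falls only if r > 1 − R/T.

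| | Cohort 1 | Cohort 2 | Cohort 3 |
|---|---|---|---|
| T/56, the ratio with no effect | 3.00 | 4.48 | 3.48 |
| Break-even reduction, R = 56 | 66.7% | 77.7% | 71.3% |
| Break-even reduction, R = 84 (assumed extension) | 50.0% | 66.5% | 56.9% |
| Count change for a true 50% fall, R = 56 | +50% | +124% | +74% |

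In the first-dose summary of SAP 6.4, with no effect, the count changes by 83/56 − 1 = +48% in Cohort 2 and 27/56 − 1 = −52% in Cohort 3.

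**2. The 6.4.1 rate.** Suppose every attack is treated. Two attacks in 56 days give 2/56 × 30.4375 = 1.087 per month. A true 50% fall gives 3.00 attacks in 168 days, 4.48 in 251 or 3.48 in 195. Each is 0.544 per month, a change of −50%. Window length cancels.

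**3. Proportion of participants requiring therapy.** The documents give neither the attack frequency nor the share of attacks treated, so both are assumed. Let attacks be Poisson with mean μ per 56 days, the same for all participants, each attack treated with probability q, and let the drug cut the rate by r. With m = μ(1 − q):

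- baseline, given at least two run-in attacks: 1 − e^(−μ)(e^m − 1 − m) / [1 − e^(−μ)(1 + μ)]
- on treatment: 1 − exp[−μq(1 − r)T/56]

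For μ = 2 and q = 0.5, m = 1 and the baseline is 1 − 0.1353 × 0.7183 / (1 − 0.1353 × 3) = 1 − 0.0972/0.5940 = 83.6%. With r = 50%, Cohort 1 gives 1 − exp(−0.5 × 3) = 77.7%.

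| μ | q | True fall | Baseline | Cohort 1 | Cohort 2 | Cohort 3 |
|---|---|---|---|---|---|---|
| 2 | 0.5 | 50% | 83.6% | 77.7% | 89.4% | 82.5% |
| 2 | 0.3 | 50% | 62.3% | 59.3% | 73.9% | 64.8% |
| 2 | 0.8 | 50% | 97.9% | 90.9% | 97.2% | 93.8% |
| 2 | 1.0 | 50% | 100% | 95.0% | 98.9% | 96.9% |
| 4 | 0.5 | 50% | 91.2% | 95.0% | 98.9% | 96.9% |
| 2 | 0.5 | 70% | 83.6% | 59.3% | 73.9% | 64.8% |
| 2 | 0.5 | 90% | 83.6% | 25.9% | 36.1% | 29.4% |

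**4. Equal windows.** With μ = 2 and q = 0.5, a 56-day window on treatment gives 1 − exp(−0.5) = 39.3% for a true 50% fall and 1 − exp(−1) = 63.2% with no effect. The gap between 83.6% and 63.2% comes from the entry criterion, not from window length.

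**The case against.** The strongest reply is that the main remedy is already planned. SAP 6.4.1 applies the monthly rate to attacks that required therapy, and 6.4.1 analyses rates against the run-in. SAP 6.4 already gives the share of attacks treated, which does not grow mechanically with time, for the run-in and first dose period, and it puts the attack rate in the same summary. Section 6.4.4 plans no change or percentage change in counts, nothing is tested, and the endpoint is by name a number, so that number belongs in the tables.

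Most of this stands, and it rules out three readings that a reader might infer:

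- That raw counts and ever-treated proportions are the whole analysis of the endpoint. They are not, because of the 6.4.1 rate.
- That the proportion of participants treated would fall artificially in Cohort 3's 27-day first dose period. The SAP lists no such output: the first-dose summary covers the number and share of attacks, and the participant proportion appears only in 6.4.4, for baseline and treatment period.
- That the baseline proportion is modest, so long windows inflate it freely. The two-attack entry criterion pushes it toward its ceiling, so the usual result is masking. If every attack is treated, reversal is impossible.

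What the reply leaves open is narrower. The 6.4.1 wording (overall rate or certain intervals) does not fix the windows for treated attacks. Section 6.4.4 neither refers to that rate nor shows days at risk. Nothing in either document time-adjusts the participant proportion.

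**Conclusion.** The point holds in a limited form and should be corrected.

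For the count, the defect is a display without exposure and without a link to the rate that corrects it. The break-even reductions of 66.7%, 77.7% and 71.3% rest on a 56-day run-in and full treatment periods; at an assumed 84-day run-in they are 50.0%, 66.5% and 56.9%.

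For the participant proportion, the defect is uncorrected. With two attacks per 56 days and half treated, a true 50% fall is largely masked in Cohorts 1 and 3 and reversed in Cohort 2. The direction depends on the assumptions: more untreated attacks or more frequent attacks extend reversal to further cohorts, while treating all attacks limits the harm to concealment. A fall of 90% would remain plain to see. These percentages assume a common Poisson rate and are illustrations, not forecasts.

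**What to change.** In SAP 6.4.4 and the matching table shells:

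- (a) State that the run-in versus treatment comparison of treated attacks uses the 6.4.1 rate per 30.4375 days, with change from run-in.
- (b) Keep the raw counts, in 6.4.4 and in the first-dose table of 6.4, and print days at risk beside them.
- (c) Add treated attacks as a percentage of all confirmed attacks for the treatment period, as 6.4 already does for the run-in and first dose period.
- (d) Report the proportion of participants requiring therapy over equal-length windows, for example the last 56 run-in days against consecutive 56-day post-dose windows, in place of run-in against the whole treatment period. That gives three full windows in Cohorts 1 and 3 and four in Cohort 2, with 195 − 168 = 27 and 251 − 224 = 27 days left over in Cohorts 3 and 2. Add a footnote that entry required two run-in attacks, since equal windows do not remove that effect.

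The cost is SAP and shell wording plus modest programming. Attack onset and on-demand treatment dates are already collected (Protocol 7.12 and 6.3.2), and the named endpoint stays in the tables.

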#### 6.4.5 HAE Attack Free Days

Descriptive statistics for the number of HAE attack free days will be provided for Baseline and on treatment. Attack Free Days may consider overlapping attacks to count any day on study without an attack. The proportion of HAE attack free days will also be provided, calculated as: the number of HAE attack free days / duration of evaluation period in days. In addition to overall post-treatment summary, the proportion of HAE attack free days will be presented in 3 month intervals and 6 months from first dose (for Cohort 1) and 6 months from *second dose* (for Cohorts 2 and 3). Additional analysis of participants who have completed each interval may be performed.

#### 6.4.6 Time to first HAE attack after first and last dosing

The time to first HAE attack will be calculated by: ( [First HAE attack or censor date] – Treatment date) +1; If a participant does not have an HAE attack, they will be censored to the end of the treatment period.

The number of participants with an HAE attack or censored will be presented. Time to first HAE attack after first dose of STAR-0215 will be presented using Kaplan-Meier estimates of 25th, 50th (median), and 75th percentiles with associated 2-sided 95% CI. The proportion of participants with their first HAE attack at 28, 56, 84, and 168 days as applicable per cohort will be calculated. The time to first HAE Attack after last dose, will be presented in the same manner.

The survival curves will be generated using the Kaplan-Meier method.

#### 6.4.7 [REDACTED].

The changes from baseline in the [REDACTED] will be presented with descriptive statistics by time point.

The [REDACTED]  
[REDACTED]

## 6.5 Pharmacokinetic pharmacodynamics (PD), immunogenicity and biomarkers Variables Evaluations

### 6.5.1 Pharmacokinetic Evaluations

Pharmacokinetic analyses will be conducted on participants in the PK Analysis Set and individual plasma concentration summary statistics will be computed using all available PK data. Assays from LC-MS/MS and ELISA will both be analyzed.

Plasma Concentrations:

Cohort 1:

Day1: Predose, 4hr (post -dose); 2, 7, 14, 28, 56, 84, 112, 140, 168 days post-dose

Cohort 2:

Day1: Predose, 4hr (post -dose); 2, 7, 14, 28, 56 day

Day 84: Predose, 4hr (post -dose); 85, 90, 97, 111, 139, 167, 209, 251 days post-initial dose

Cohort 3:

Day1: Predose, 4hr (post -dose); 2, 7, 14 day

Day28: Predose, 4hr (post -dose); 29, 34, 41, 55, 83, 111, 153, 195 days post-initial dose

Individual plasma STAR-0215 concentration data will be listed for each participant and summarized by nominal sampling time point and visit as applicable with descriptive statistics as described below.

Plasma concentrations below the limit of quantification (BLQ) will be flagged as BLQ in the concentration and parameters tables and considered to be 0 for PK and descriptive statistical analysis. BLQ values in between two measurable concentrations will be treated as missing.

If more than 50% of values are below the LLOQ, the mean and standard deviation will be shown as not calculable (NC), and the minimum value will be shown as BLQ. BLQ values between two measurable concentrations are treated as missing. Missing values will be omitted from the calculation of descriptive statistics. Number of missing values will be reported in descriptive statistics.

Individual plasma concentration-time data will be displayed graphically, summarized, and listed. Individual plasma concentrations below the LLOQ will be graphed as  $\frac{1}{2}$  LLOQ.

Plasma concentrations will be summarized by visit / timepoint including all sample assessments. The following descriptive statistics will be presented for plasma concentrations obtained at each nominal time point. n (number of non-missing observations), arithmetic mean(AM), SD, median, Q1, Q3, minimum, maximum, geometric mean, geometric CV, where  $GCV\% = \sqrt{\exp(s^2) - 1} * 100$  and s is the standard deviation of the log-transformed values.

Plasma concentrations vs. time will be displayed graphically in linear and semi-log scale using arithmetic mean and geometric mean. Nominal sampling times will be used in the table summaries and summary figures of plasma concentrations.

### Non-Compartmental Analysis:

Pharmacokinetic analyses will be conducted using the PK Set. PK parameters of STAR-0215 will be analyzed based on the actual sampling times. When actual times are not available, nominal times will be used instead if deemed appropriate by the pharmacokineticist.

All parameters will be derived using model-independent methods (non-compartmental analysis – NCA) as implemented in Phoenix® WinNonlin® version 8 or higher (Certara USA Inc., Princeton, New Jersey).

The following PK parameters will be calculated for STAR -0215 based on all available samples:

### Cohort 1 Day 1:

Parameter (Units)	CDISC TERM	Definition	Method of Determination
AUC0-t*	AUCLST	AUC from time zero to time t of the last measured quantifiable concentration calculated using the linear-up/logarithmic-down trapezoidal method	Calculated using the linear up/log down variant of the trapezoidal rule
AUC0-∞	AUCIFP	Area under the concentration versus time curve from 0 to infinity	Calculated as AUC0-last + Cest,last/λz, where Cest,last is the estimated last measurable concentration and AUC0 last is the area under the concentration-time curve from 0 to the time of the last quantifiable (above LLOQ) sample after dosing

			(calculated using the 'linear up, log down' calculation method )
Cmax	CMAX	maximum observed plasma concentration	Observed value
tmax	TMAX	time to reach Cmax	Observed value
Cavg #	CAVG	Average Concentration	AUCTAU divided by TAU
t 1/2	LAMZHL	apparent terminal half-life	ln(2)/ λ z , where λ z is the apparent first-order terminal elimination rate constant. At least three consecutive time points (excluding Cmax) in the terminal phase will be used for apparent terminal half-life determination, with an R  value of 0.85 or greater

\* AUC(0-t) = AUC from time zero to last quantifiable time-point or 168 days

# The value of Tau used for this analysis is 168 days

#### Cohort 2 Dose 1:

Parameter (Units)	CDISC TERM	Definition	Method of Determination
AUC0-84	AUCINT	The area under the curve (AUC) over the interval from 0 to 84 day.	Calculated using the linear up/log down variant of the trapezoidal rule
Cmax	CMAX	maximum observed plasma concentration	Observed value
tmax	TMAX	time to reach Cmax	Observed value

Cavg #	CAVG	Average Concentration	AUCTAU divided by TAU
-------------------	------	-----------------------	-----------------------

#The value of Tau used for this analysis is 56 days

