9.5. Pharmacokinetic Analysis

Pharmacokinetic analyses will be conducted on participants in the PK Analysis Set.

Pharmacokinetic parameters will be listed by participant and summarized by dose group using descriptive statistics.

STAR-0215 PK parameters will be computed, when data allow, using standard noncompartmental methods based on observed STAR-0215 concentrations and on actual sample collection times. The following noncompartmental PK parameters, when data allow, will be calculated and reported:

- Maximum drug concentration (C_{\max})
- Time of C_{\max} (T_{\max})
- Area under the curve (AUC) after a defined duration or at steady state
- Circulating half-life ($t_{1/2}$)
- Apparent clearance (CL/F)
- Volume of distribution (V/F)

Individual blood concentrations of STAR-0215 will be plotted by actual time on both linear and semi-logarithmic scales. Mean blood concentrations will be plotted by nominal time and on both linear and semi-logarithmic scales. A preliminary assessment of dose proportionality will be made by examining plots of dose-normalized AUC and C_{\max} values versus the STAR-0215 dose. When data allow, accumulation will be assessed.

Full details of the PK analysis and modeling approach will be provided in the SAP or a separate PK analysis plan as appropriate.

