#### 3.3 Secondary Endpoints - Pharmacokinetic, Pharmacodynamics (PD) and immunogenicity

- Concentration of STAR-0215 and the derived PK parameters
  - Maximum drug concentration (Cmax)

- Time of Cmax (Tmax)
- Area under the curve (AUC) after a defined duration or at steady state
- Circulating half-life ( $t_{1/2}$ )
- Apparent clearance (CL/F)
- Volume of distribution (V/F)
- Change in plasma kallikrein activity (PD)
- Formation of anti-drug (STAR-0215) antibodies

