## 6 STATISTICAL METHODS

### 6.1 Sample Size Justification

This is the first time STAR-0215 is being used in participants with HAE. No formal sample size calculations have been performed.

Up to 28 participants will be dosed in this study. This is considered adequate to characterize the safety, tolerability, clinical activity, PK, PD, and immunogenicity of STAR-0215.

No placebo group will be used in this study; each participant will serve as their own control. Data collected during the Run-In period will be used to establish each participant's baseline.

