**Cohort 2 Dose 2:**

Parameter (Units)	CDISC TERM	Definition	Method of Determination
AUC84-251	AUCINT	The area under the curve (AUC) over the interval from 84 to 251 day.	Calculated using the linear up/log down variant of the trapezoidal rule
AUC0-251	AUCINT	The area under the curve (AUC) over the interval from 0 to 251 day.	Calculated using the linear up/log down variant of the trapezoidal rule
AUC0- $\infty$	AUCIFP	Area under the concentration versus time curve from 0 to infinity	Calculated as AUC0-last + Cest,last/ $\lambda_z$ , where Cest,last is the estimated last measurable concentration and AUC0 last is the area under the concentration-time curve from 0 to the time of the last quantifiable (above LLOQ) sample after dosing (calculated using the 'linear up, log down' calculation method )
Cmax	CMAX	maximum observed plasma concentration	Observed value
tmax	TMAX	time to reach Cmax	Observed value
Cavg #	CAVG	Average Concentration	AUCTAU divided by TAU
CL/F *	CLFP	total clearance	Calculated as CLFP = Dose/ AUC0- $\infty$

$t_{1/2}$	LAMZHL	apparent terminal half-life	$\ln(2)/\lambda_z$ , where $\lambda_z$ is the apparent first-order terminal elimination rate constant. At least three consecutive time points (excluding $C_{max}$ ) in the terminal phase will be used for apparent terminal half-life determination, with an $R^2$ value of 0.85 or greater
-----------	--------	-----------------------------	-----------------------------------------------------------------------------------------------------------------------------------------------------------------------------------------------------------------------------------------------------------------------------------------------

\*Computed using the AUC(0-inf) over both doses

#The value of Tau used for this analysis is 168 days

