**Cohort 3 Dose 2:**

Parameter (Units)	CDISC TERM	Definition	Method of Determination
AUC0-195	AUCINT	The area under the curve (AUC) over the interval from 0 to 195 day.	Calculated using the linear up/log down variant of the trapezoidal rule
AUC28-195	AUCINT	The area under the curve (AUC) over the interval from 28 to 195 day.	Calculated using the linear up/log down variant of the trapezoidal rule

AUC 0-∞	AUCIFP	Area under the concentration versus time curve from 0 to infinity	Calculated as AUC 0-last + C est,last /λ z , where C est,last is the estimated last measurable concentration and AUC 0 last is the area under the concentration-time curve from 0 to the time of the last quantifiable (above LLOQ) sample after dosing (calculated using the 'linear up, log down' calculation method )
C max	C MAX	maximum observed plasma concentration	Observed value
t max	T MAX	time to reach C max	Observed value
C avg #	CAVG	Average Concentration	AUCTAU divided by TAU
CL/F *	CLFP	total clearance	Calculated as CLFP = Dose/ AUC 0-∞
t 1/2	LAMZHL	apparent terminal half-life	ln(2)/ λ z , where λ z is the apparent first-order terminal elimination rate constant. At least three consecutive time points (excluding C max ) in the terminal phase will be used for apparent terminal half-life determination, with an R  vale of 0.85 or greater

#The value of Tau used for this analysis is 195 days

\*CL/F computed over the entire time-course of concentrations

In addition to summarization by cohort and dose, the calculated PK parameters will also be summarized by ADA status and dose cohort provided in the dataset. A participant will be considered ADA-positive if, at any time during the dosing interval, anti-drug antibodies are detected. Similarly, treatment-emergent ADA status will be used to summarize PK parameters.

PK parameters will also be summarized graphically by ADA status and dose cohort with either box plots or scatter plots depending on the amount of data.

The AUC parameters will be calculated using the linear trapezoidal method for ascending concentrations and the log trapezoidal method for descending concentrations ('linear up, log down') calculation method option in WinNonlin.

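### SAP 6.5.1 sets tau for average concentration on no single convention (56 days for an 84-day interval, 195 against 168 after Dose 2) and leaves the dose in CL/F undefined

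*SAP*

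**What the plan says.** SAP 6.5.1 gives one non-compartmental parameter table per cohort and dose. Cavg is "AUCTAU divided by TAU" throughout. The area over tau has no row of its own, and its start and end are not stated.

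- Cohort 1: tau is 168 days.
- Cohort 2 Dose 1: the tabulated area is "The area under the curve (AUC) over the interval from 0 to 84 day", but the footnote reads "The value of Tau used for this analysis is 56 days".
- Cohort 2 Dose 2: AUC84-251 and AUC0-251 are listed, and tau is 168 days.
- Cohort 3 Dose 1: there is no Cavg row.
- Cohort 3 Dose 2: AUC28-195 and AUC0-195 are listed, and the footnote reads "The value of Tau used for this analysis is 195 days".

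CL/F appears only in the two Dose 2 tables, as dose over AUC0-∞. The Cohort 2 footnote says "Computed using the AUC(0-inf) over both doses", and the Cohort 3 footnote says the entire time course is used. Neither says which dose is the numerator. SAP 3.3 and Protocol 9.5 list CL/F and V/F among the PK parameters without limiting them to particular cohorts.

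**The concern.** An average over a dosing interval should use the length of that interval, and the same label should mean the same quantity in each cohort. Here 56 days matches neither the time to the second dose nor the area reported beside it, and the two Dose 2 tables appear to count from different doses. The weeks left out in Cohort 2 come just before the second dose, when concentrations are lowest. Protocol 2.4 justifies that regimen by its effect on minimum concentrations.

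For CL/F, the tables are headed Dose 2 but the denominator covers both doses. An analyst working from the Cohort 2 Dose 2 table could reasonably enter 300 mg.

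Derived PK parameters are a secondary endpoint, and Protocol 9.12 says PK results may inform the decision to enlarge Cohorts 2 and 3. Two competent analysts should not be able to get different values from the same data.

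**Working it through.** **Inputs.** Tau and AUC windows are from the SAP 6.5.1 tables. Dosing days and amounts are from SAP Table 2: Cohort 1, 450 mg on Day 1; Cohort 2, 600 mg on Day 1 and 300 mg on Day 84; Cohort 3, 600 mg on Days 1 and 28. Protocol 2.1.4.2 blacks out the animal half-lives and no human value is given, so I assume a half-life of 20 to 120 days and ka of 0.15 to 0.6 per day.

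**Step 1: can each tau be reproduced?** Elapsed days are end minus start; inclusive days add one.

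| Window | Elapsed | Inclusive | Stated tau | Match |
|---|---|---|---|---|
| Cohort 1, Day 1 to 168 | 167 | 168 | 168 | yes |
| Cohort 2 Dose 1, Day 1 to 84 | 83 | 84 | 56 | no |
| Cohort 2 Dose 2, Day 84 to 251 | 167 | 168 | 168 | yes |
| Cohort 2 whole course, Day 1 to 251 | 250 | 251 | 168 | no |
| Cohort 3 Dose 2, Day 28 to 195 | 167 | 168 | 195 | no |
| Cohort 3 whole course, Day 1 to 195 | 194 | 195 | 195 | yes |

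In the order of the tables, per-dose intervals would give about 168, 84, 168 and 168. Whole-course windows would give 168, 251 and 195 for Cohorts 1, 2 and 3. The stated 168, 56, 168 and 195 follow neither. The visit window of ±3 days puts Dose 2 of Cohort 2 on Days 81 to 87, so it does not explain 56. The only match I find is the last sample listed under the Cohort 2 Day 1 dose in SAP 6.5.1. The next sample, Day 84 pre-dose, is listed under the second dose.

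**Step 2: size in Cohort 2 Dose 1, read as AUC0-56/56.** I use a linear one-compartment model with first-order absorption and ke = ln 2 / half-life. Up to a factor that cancels,

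AUC(0,T) ∝ (1 − e^(−ke·T))/ke − (1 − e^(−ka·T))/ka.

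Worked case, half-life 60 days and ka 0.3 (ke = 0.01155):

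- T = 56: 41.23 − 3.33 = 37.90, and 37.90/56 = 0.677.
- T = 83: 53.38 − 3.33 = 50.05, and 50.05/83 = 0.603.
- Ratio: 1.122.

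Across ka from 0.15 to 0.6 the ratio is:

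| Half-life (days) | 56-day mean / 83-day mean |
|---|---|
| 20 | 1.301 to 1.336 |
| 30 | 1.212 to 1.251 |
| 60 | 1.097 to 1.134 |
| 90 | 1.053 to 1.089 |
| 120 | 1.030 to 1.065 |

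The excess is therefore 3% to 34%.

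**Step 3: Cohort 3 Dose 2 under each reading of 195.**

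- AUC0-195/195 is a valid whole-course mean. In the same model it is 0.944 to 1.217 times the post-Dose 2 mean (−6% to +22%).
- AUC28-195/195 would be 167/195 = 0.856 of the post-Dose 2 mean, 14% low.
- Counting 195 days from Dose 2 would run about 28 days past the last scheduled PK sample (28 + 195 = 223, against Day 195). It would give 0.858 to 0.938 of the post-Dose 2 mean.

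**Step 4: CL/F.** Under linear kinetics AUC0-∞ over both doses equals F × (dose 1 + dose 2)/CL, so only the total dose recovers CL/F. Totals are 600 + 300 = 900 mg (Cohort 2) and 600 + 600 = 1200 mg (Cohort 3).

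- Cohort 2 with 300 mg: 300/900 = 0.33 of the true value.
- Cohort 2 with 600 mg: 600/900 = 0.67.
- Cohort 3 with 600 mg: 600/1200 = 0.50.

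These ratios do not depend on the assumed half-life or ka.

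**Step 5: tables against the parameter list.** Cohort 1 has an AUC0-∞ row but no CL/F row. V/F is in no table.

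**The case against.** The strongest reply is that nothing here is shown to be miscalculated, and much of it stands.

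- A reader might infer that AUC0-84 is divided by 56, which would inflate Cavg by half (84/56 = 1.50). The SAP does not prescribe that. Its formula takes the area over tau, most naturally AUC0-56, which gives a valid 56-day mean.
- A reader might infer that 195 is applied to the 167-day interval after Dose 2, giving the 14% error. The same table lists AUC0-195, which 195 fits, so a whole-course average under a Dose 2 heading is the likelier explanation. The pairing with AUC28-195 is stated nowhere.
- A reader might infer that CL/F is wrong. Both footnotes disclose the two-dose area, and with the total dose the ratio is correct and comparable between Cohorts 2 and 3. It is ambiguous, not wrong.
- The gap between 167 and 168 days is day numbering and immaterial.

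On importance, Cavg is not among the parameters named in Protocol 9.5 or SAP 3.3. AUC0-84 is reported and the Day 84 pre-dose concentration is summarised, so the full-interval average can be recovered. Results are descriptive and by cohort, and no cross-cohort comparison of Cavg is planned.

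On omissions, Protocol 9.5 says "A preliminary assessment of dose proportionality will be made by examining plots of dose-normalized AUC" and Cmax against dose, and SAP 6.5.1 does not repeat it. But the protocol permits a separate PK analysis plan and makes accumulation and the parameters conditional on the data, so I do not count those as established gaps. V/F and Cohort 1 CL/F differ because the SAP lists both parameters itself and then does not tabulate them.

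What survives is that 56 does not match the interval, the two Dose 2 averages are different quantities under one name, and the dose is undefined.

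**Conclusion.** The point holds as an inconsistency of definition, and it should be fixed. Tau of 56 days is not the Cohort 2 dosing interval, and sampling does not force it because a Day 84 pre-dose sample is taken. On the natural reading Cavg lies 3% to 34% above the interval average, a range that rests wholly on the assumed half-life, ka and linear one-compartment model. That the two Dose 2 averages are not comparable follows from the SAP's own day labels. The CL/F factors of 0.33, 0.67 and 0.50 need only linear kinetics, but they arise only if someone enters a single dose.

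The documents do not support saying that Cavg and CL/F are wrong as planned, or that a 50% or 14% error is built in. No hypothesis test or primary endpoint is affected.

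**What to change.** In the SAP 6.5.1 tables:

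1. State the start and end of the area used for Cavg in each table.
2. For Cohort 2 Dose 1, use AUC0-84 over the matching interval (84 days nominal, 83 elapsed).
3. For Dose 2 in both cohorts, use the same post-Dose 2 window: AUC84-251 and AUC28-195, each over about 167 days. If AUC0-195/195 is kept, label it a whole-course average.
4. State that the dose in CL/F is the total administered dose whenever AUC0-∞ spans both doses.
5. Add the CL/F row for Cohort 1 and V/F rows, or declare in SAP Section 7 that they were dropped.

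The cost is edits to tables and footnotes and a re-run of the non-compartmental analysis. No new samples or visits are needed.
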